## Study protocol and analysis plan

This proposal focuses on screening and treatment referral specifically among adolescents. In the proposed study, we will train PC clinicians (e.g., nurses) in four clinics across two states to use the new two-question NIAAA screening guide (NIAAA SG) to determine the prevalence of at-risk alcohol use among an ethnically and racially diverse group of youth age 12-18, and to test the feasibility and practicality of this brief screener for predicting subsequent alcohol use, alcohol risk and problems among this population. In addition, we will examine how well the NIAAA SG questions identify other behavioral health problems, including cigarette and marijuana use, sexual risk behavior, delinquency and conduct disorder.

Youth identified as at-risk according to the NIAAA SG will receive a brief motivational interviewing (MI) intervention as recommended by the guide.

### **Our specific aims are:**

**Aim 1:** Use the NIAAA SG to screen 2000 ethnically and racially diverse adolescents age 12-18 in four PC clinics and assess the prevalence of youth who screen positive for at-risk alcohol use in this setting. We will compare prevalence across the NIAAA screening guide, and other highly used screening measures, such as the Problem Severity Scale (PS) on the PESQ, the AUDIT and the CRAFFT.

**Aim 2a:** Compare the NIAAA SG and the PESQ-PS, AUDIT and CRAFFT against a gold standard of DSM diagnosis of abuse or dependence to determine each screener's utility, sensitivity and specificity as a predictor of alcohol risk, use, and problems in this population at baseline and at six months.

**Aim2b:** Compare the NIAAA SG to the PESQ-PS, AUDIT and CRAFFT to determine each screener's utility, sensitivity and specificity as an initial screen for other behavioral health problems, including marijuana use, cigarette smoking, sexual risk behavior, delinquency, and conduct disorder at baseline and at six months.

**Aim 3a:** Use the NIAAA SG to identify youth who are at moderate and high risk. Provide a brief MI intervention in the PC setting to adolescents who screen in at moderate or high risk based on the guide and examine whether alcohol use and problems decrease over a one year period for these youth compared to youth at moderate or high risk who receive enhanced usual care.

**Aim 3b:** Explore whether there is differential effectiveness of the intervention depending upon risk level.

### **Recruitment protocol**

All adolescents who have appointments at the clinic and are between the age of 12 and 18 will be screened by clinic staff using the NIAAA screening guide. We expect to screen approximately 2000 youth. After completion of the screener and their PC appointment, clinic staff will ask youth to be part of a study to complete a web-based baseline and six month survey. Those who agree will complete additional surveys. Teens must have parental consent if they are under 18 and must also assent. Based on our previous experiences in survey studies with youth, we expect 90% of youth to agree to complete the surveys. If a teen would like to participate, but the parent is not present, we will follow-up with that teen to obtain parental consent and then schedule a time for him or her to return to the clinic. At the 6 month follow up we will survey all individuals who were screened as high risk (estimated 25%). We will follow-up with a randomly selected 40% of individuals screened as low risk (assuming that 75% were low risk); we will therefore follow up

810 individuals, which still provides us with ample power to test our hypotheses (see Power section) and keeps project costs down. Youth who screen in at moderate or high risk on the NIAAA SG will be told that they are eligible to participate in additional surveys at three months and 12 months, and that they have an opportunity to obtain additional information on AOD use if they are interested. They will then complete an additional section of the consent/assent form that details the additional surveys and randomization to CHAT (our brief motivational interviewing intervention) or enhanced usual care (EUC) (if under 18, they must also have parental consent). As noted above, all youth will complete a web-based baseline survey on site and a six month follow up web survey. Youth who are part of the randomized trial will also complete follow-up web-based surveys at 3 months and 12 months. Half of the youth will receive the CHAT MI session, which is delivered in 15-20 minutes and is reinforced with a 5-10 minute MI booster phone call one month later that follows up on information discussed during the session. EUC: Since usual care may differ slightly across the sites, similar to other work in this area, we will provide an EUC condition for the other youth. EUC will be designed to replicate current practice, which generally consists of teens getting screened for AOD use and 'yes' responses being queried further and followed by some brief discussion (personal communication from clinic directors). EUC participants will also be provided with a brochure from our staff, similar to the brochure for the MI intervention, and they will be asked to review it. Given the extra burden of the two additional surveys and staying to receive EUC or CHAT, we conservatively estimate that of those who are eligible for Aim 3, 70% will agree to participate and will have parental consent.

### **Statistics**

Analyses for Aim 1 are primarily descriptive. We will calculate prevalence scores for each level of each of the four measures (NIAAA SG, PESQ-PS, AUDIT, CRAFFT), and calculate confidence intervals of those rates of prevalence. We will explore prevalence differences across location, gender, age and race/ethnicity using each measure in a logistic regression.

We will examine differences in outcomes between the two groups at 3-, 6-, and 12-months follow-up. We will also examine rates of change over time using a growth modeling procedure. This procedure will allow us to examine overall trajectories of differences in cognitions or behaviors. We will use appropriate modeling techniques for continuous outcome variables and categorical outcome variables. We will employ facilitator as a fixed factor (i.e. dummy coded), as facilitators are involved in both CHAT and EUC conditions. Controlling for facilitator also has the effect of controlling for location. We will use full information maximum likelihood (FIML) estimation to account for attrition.

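### The 3-, 6- and 12-month CHAT–EUC contrasts name only facilitator as a covariate; pre-specifying the baseline value of the outcome would sharpen them at no data cost

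*Combined protocol and SAP*

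**What the plan says.** The Aim 3a analysis text, at the end of the section Overview of follow up for Aims 2 and 3, lists two analyses. The first is the set of time-point contrasts: "We will examine differences in outcomes between the two groups at 3-, 6-, and 12-months follow-up". The second is added to it: "We will also examine rates of change over time using a growth modeling procedure".

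On covariates it says: "We will employ facilitator as a fixed factor (i.e. dummy coded), as facilitators are involved in both CHAT and EUC conditions", and then "Controlling for facilitator also has the effect of controlling for location". No other covariate is named, and none is excluded. On missing data it says: "We will use full information maximum likelihood (FIML) estimation to account for attrition".

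The baseline data are planned elsewhere. In the Recruitment protocol, "all youth will complete a web-based baseline survey on site", and "Youth who are part of the randomized trial will also complete follow-up web-based surveys at 3 months and 12 months". Aim 2a assesses each screener "as a predictor of alcohol risk, use, and problems in this population at baseline and at six months". The Aim 3b text uses baseline severity again, but as a modifier of the intervention effect.

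The supplied text gives no Aim 3 sample size, effect size, power or baseline-to-follow-up correlation. The Recruitment protocol refers to a Power section that is not in that text, so what it assumed cannot be seen.

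**The concern.** The trial enrols youth selected on alcohol risk and follows alcohol use and problems for a year. Where a participant's baseline level predicts the later level, a contrast that ignores baseline leaves explainable variation in the error term. Facilitator, and location through it, does not stand in for the individual's own starting level.

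Two things are at stake.

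- **Precision** of the trial's main efficacy comparison, with only about 270 to 300 completers.
- **Pre-specification.** The text is silent on baseline, so adjusted or unadjusted results could be chosen after the data are seen, at three time points and for several outcomes.

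Having baseline in the likelihood would also protect FIML against dropout that relates to baseline differently by arm. The documents give no sign that such dropout is expected, so no bias is claimed.

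**Working it through.** The plan has no figure of its own to reproduce here, so the check starts from its stated rates.

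**Inputs from the documents.** About 2000 screened, 90% agreeing to surveys and 25% at risk (Recruitment protocol); 70% of eligible youth joining the trial and half allocated to CHAT (Recruitment protocol); 85% completing six months (Overview of follow up for Aims 2 and 3).

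**Assumptions.** Two-sided 5%, 80% power, 85% retention also at 3 and 12 months, and baseline-to-follow-up correlation r = 0.3, 0.5 or 0.7.

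**Step 1: trial size, two readings.**

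- With the 90% applied first: 2000 × 0.90 × 0.25 × 0.70 = 315 randomised; × 0.85 = 267.75, about 268 completers.
- Without it: 2000 × 0.25 × 0.70 = 350 randomised; × 0.85 = 297.5, about 298 completers.

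**Step 2: simple contrast, continuous outcome.** In SD units, the detectable difference is (1.960 + 0.842) × √(4/n). Adjusting for baseline multiplies it by √(1 − r²).

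| Completers | Unadjusted | r = 0.3 | r = 0.5 | r = 0.7 |
|---|---|---|---|---|
| 268 | 0.342 | 0.327 | 0.297 | 0.245 |
| 298 | 0.325 | 0.310 | 0.281 | 0.232 |
| Reduction, 1 − √(1 − r²) | – | 4.6% | 13.4% | 28.6% |

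Put another way, with 268 completers and an assumed true difference of 0.3 SD, power is 69% unadjusted and 73%, 81% or 93% adjusted. At r = 0.5 the gain equals having 268/(1 − 0.25) ≈ 357 completers.

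**Step 3: the comparator closest to the plan.** FIML on three follow-ups already borrows some information across waves, so the fair question is what baseline adds to that. The precision of the 12-month arm contrast was taken from the expected information of a Gaussian likelihood. Each wave had 15% missing at random, and facilitator dummies were in both models (4 facilitators explaining 0% of the variance or 8 explaining 5%, assumed). Correlations were either equal or decaying with time, with the baseline-to-12-month value set to r. Ranges are over these settings.

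| Randomised | r | No baseline (SD) | With baseline (SD) |
|---|---|---|---|
| 315 | 0.3 | 0.329–0.341 | 0.315–0.327 |
| 315 | 0.5 | 0.324–0.336 | 0.284–0.295 |
| 315 | 0.7 | 0.319–0.330 | 0.233–0.242 |
| 350 | 0.3 | 0.312–0.323 | 0.299–0.310 |
| 350 | 0.5 | 0.308–0.319 | 0.269–0.280 |
| 350 | 0.7 | 0.303–0.313 | 0.221–0.230 |

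The reductions are 4.0–4.2%, 12.2–12.4% and 26.6–27.1%. FIML on the follow-ups alone therefore does not already deliver the gain.

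**Step 4: binary outcome.** This was simulated with 315 randomised, three waves, 15% missing at random per wave, 50% prevalence and 6 facilitators explaining 5% of the variance (all but the 315 assumed). The model was a logistic GEE, standing in for a likelihood fit. The measure is the standardised 12-month risk difference; the detectable difference is 2.802 × SE.

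| r | SE: none / score / yes-no baseline | Detectable difference (points) | Reduction: score / yes-no |
|---|---|---|---|
| 0.3 | 0.0590 / 0.0575 / 0.0583 | 16.5 / 16.1 / 16.3 | 2.5% / 1.2% |
| 0.5 | 0.0600 / 0.0549 / 0.0571 | 16.8 / 15.4 / 16.0 | 8.5% / 4.8% |
| 0.7 | 0.0594 / 0.0486 / 0.0523 | 16.6 / 13.6 / 14.6 | 18.2% / 12.0% |

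Monte Carlo error on these percentages is about 1 to 2 points, so the r = 0.3 row is barely distinguishable from no gain. Count outcomes were not simulated.

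The scale matters. In a separate simulation of a single binary time point (268 analysed), the SE of the log odds ratio rose with adjustment, from 0.263 to 0.290 at r = 0.5, because the conditional odds ratio is a different estimand. The SE of the risk difference fell from 0.0575 to 0.053.

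**The case against.** The strongest objection is that the plan probably uses baseline already. Aim 3a asks about change over one year, and follow-ups at 3, 6 and 12 months span only nine months, so baseline is naturally the first wave of the growth model. With complete data, equal correlations and a linear trend, such a model with a common starting mean gives a 12-month contrast variance of 0.84, 0.71 and 0.48 of the unadjusted value at r = 0.3, 0.5 and 0.7. Baseline adjustment gives 0.91, 0.75 and 0.51. These figures are right, but they depend on specification: with free starting means, the slope contrast gives 1.28, 0.91 and 0.55. They also concern the second listed analysis. They do not put baseline into the separately listed time-point contrasts.

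It is also fair to say that the text is brief, facilitator is mentioned for a design reason, and silence is not exclusion. That is accepted; the point is that the choice should not be left open.

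Other limits stand. The contents of the baseline survey are not listed, so its availability is well supported for alcohol use and problems but not documented for every outcome, such as the cognitions mentioned under Aim 3a. The correlation is unknown, and enrolling only moderate- and high-risk youth may lower it. Unadjusted contrasts remain valid under randomisation.

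**Conclusion.** The concern holds, as an efficiency and pre-specification point and not as an error or a bias. The time-point contrasts are listed apart from the growth model, facilitator is the only covariate named for them, and baseline alcohol measures are planned for everyone. Against the nearest reading of the plan without baseline, adding it lowers the 12-month detectable difference by about 4%, 12% or 27% for a continuous outcome at r = 0.3, 0.5 or 0.7. For a binary outcome with a baseline score the gain is about 3%, 8% and 18%, and it is less with a yes/no baseline. The size rests on the assumed correlation, power, significance level, prevalence, facilitator effects and 12-month retention. It is worthwhile at moderate or high correlation and small at 0.3. The change should be made; confidence in the size of the benefit is medium.

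**What to change.** Add to the Aim 3a analysis text a sentence such as: *The CHAT–EUC contrasts at 3, 6 and 12 months will be estimated from one joint longitudinal model of all follow-up waves fitted by FIML, with arm, wave, arm-by-wave, the baseline value of the outcome with its wave interaction, and facilitator. Binary and count outcomes will use the same terms with the matching link and will be reported as marginal contrasts.*

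The text should also say whether baseline is a wave in the growth model, and which baseline measure serves any outcome not collected at baseline. NIAAA SG risk level may be added, but no material precision gain is claimed for it.

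The cost is the added text, three extra parameters per outcome (baseline by wave) and a standardisation step for binary and count outcomes. No visits, participants, measures or burden are added.
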